ANNEX 3.3: DEFINITIONS OF STUDY COVARIATES

Complete list of ICD-9-CM, ICD-10, CPT, HCPCS, and GPI codes.

Medication	HCPCS	GPI
Short-acting beta- agonists		
Levalbuterol	J7617,J7607,J7612,	4420104510X
	J7614,J7615	4420104550X
Albuterol	J7602, J7603,	4420101000X
	J7609-J7611,	4420101010X
	J7613, J7616,	
	17625 04093	
	Q4094	
Terbutaline	J3105,J7680,J7681	442010602X
Isoproterenol	J7657	44201040X
	J7658	
	J7659	
	J7660	
Methylxanthines		
Aminophylline		4430001000x
		4430001010x
Theophylline (SR)	J2810	4430004000x 499100240X
		4499100220X
		4499100242X 4499100250X
		44992203A 44002003X 44002204X 44000003X
		44995005A 44995204A 44999005A 44000602X 4400220310X
		4499960270X
		4499220315X

Boehringer Ingelheim		
Protocol for non-interventional	studies based of	n existing data
BI Study Number 1237-0094		

Medication	HCPCS	GPI
SAMA (Short-acting muscarinic antagonists)		
Ipratropium bromide	J7644, J7655	4230X 44100030X
Antibiotics for a respiratory condition		
Aamikacin	J0278	07000010x
Amoxicillin/potassium clavulanate		0199000220x
Amoxicillin		01200010x
Ampicillin	J0290	01200020x
Ampicillin-sulbactam	J0295	0199000225x
Azithromycin	J0456	03400010x
Aztreonam	S0073	16000005x
Cefaclor		02200040x
Cefdinir		02300040x
Cefepime	J0692	02400040x
Cefixime		02300060x
Cefotaxime	J0698	02300075x
Cefpodoxime		02300065x
Cefprozil		02200062x
Ceftazidime	J0713, J0714	02300080x
Ceftriaxone	J0696	02300090x
Cefuroxime	J0697	02200065x
Ciprofloxacin	J0744	05000020x
Clarithromycin		03500010x
Doxycycline		04000020x
Ertapenem	J1335	16150030x
Erythromycin	J1364	0310x
Gemifloxacin		05000083x
Imipenem	J0743	16159902x
Levofloxacin	J1956	05000034x
Linezolid	J2020	16230040x

 Study Number 1237-0094
 c30699487-01

 Proprietary confidential information © 2019 Boehringer Ingelheim International GmbH or one or more of its affiliated companies

Medication	HCPCS	GPI
Meropenem	J2185	16150050x
Moxifloxacin	J2280	05000037x
Penicillin G benzathine	J0561, J0558	01990002x, 01100020x
Penicillin VK		01100040x
Piperacillin	S0081	01400040x
Piperacillin-tazobactam	J2543	019900027x
Procaine penicillin	J0558, J2510	
Ticarcillin		01400050x
Ticarcillin-clavulanate	S0040	019900023x
Trimethoprim- sulfamethoxazole	S0039	169900023x
Vancomycin	J3370	16000060102x

Condition	ICD9	ICD10	ICD9	ICD10 proc	HCPC	CPT
			proc		S	
Asthma	493	J45				
	493	J45.2				
	493	J45.20				
	493.01	J45.21				
	493.02	J45.22				
	493.1	J45.3				
	493.1	J45.30				
	493.11	J45.31				
	493.12	J45.32				
	493.2	J45.4				
	493.2	J45.40				
	493.21	J45.41				
	493.22	J45.42				
	493.8	J45.5				
	493.81	J45.50				
	493.82	J45.51				

Boehringer Ingelheim		
Protocol for non-interventional	studies based	on existing data
BI Study Number 1237-0094		

Condition	ICD9	ICD10	ICD9 proc	ICD10 proc	HCPC S	CPT
	493.9	J45.52				
	493.9	J45.9				
	493.91	J45.90				
	493.92	J45.901				
		J45.902				
		J45.909				
		J45.99				
		J45.990				
		J45.991				
		J45.998				
Lung cancer	162	C33				
_	231.2	C34.00				
	197.0	C34.10				
	176.4	C34.2				
	235.7	C34.30				
	V10.11	C34.80				
		C34.90				
		C46.50				
		C78.00				
		D02.20				
		D38.1				
		Z85.118				
Interstitial	516.6*	J84.115				
lung disease	516.34	J84.83				
		J84.841				
		J84.842				
		J84.843				
		J84.848				
Lung			33.50	0BYC0Z0	S2060	00580
transplant			33.51	0BYC0Z1	S2061	32850
			33.52	0BYC0Z2		- 32856
				0BYD0Z0		33935
				0BYD0Z1		33933

Proprietary confid	iential information © 201	9 Boehringer Ingelhein	n International G	mbH or one or more of	its affiliated co	ompanies
Condition	ICD9	ICD10	ICD9 proc	ICD10 proc	HCPC S	СРТ
				0BYD0Z2		
				0BYF0Z0	-	
				0BYF0Z1	-	
				0BYF0Z2	-	
				0BYG0Z0		
				0BYG0Z1		
				0BYG0Z2		
				0BYH0Z0		
				0BYH0Z1		
				0BYH0Z2		
				0BYJ0Z0		
				0BYJ0Z1		
				0BYJ0Z2		
				0BYK0Z0	-	
				0BYK0Z1	-	
				0BYK0Z2		
				0BYL0Z0		
				0BYL0Z1		
				0BYL0Z2		
				0BYM0Z0	_	
				0BYM0Z1		
				0BYM0Z2		
Cardiovascul ar disease	410.xx- 414.xx 427.xx; 785.0; 785.1 426.xx 428.xx 401.xx- 405.xx 440.xx; 441.xx; 442.xx;	I20.%- I25.%%% I47.%, I48.%%; I49.%% I44.%%; I45.%% I50.%% I11.%; I13.%; O10.1%; O10.3%	37.7x– 37.8x, 37.94– 37.99			

c30699487-01

Boehringer Ingelheim				
Protocol for non-interventional	studies based	l on	existing da	ata
BI Study Number 1237-0094			_	

Condition	ICD9	ICD10	ICD9 proc	ICD10 proc	HCPC S	CPT
	443.xx 272.x 393-398; 421.x; 422.xx; 746.0x-746.7	I70.%%%; I71.%%; I72.%; I73.%% E78.%% I05.%- I09.%%; I33.%-I39; Q22.%, Q23.%				
Diabetes	250	E10.10				
	250.01	E10.11	-			
	250.02	E10.21				
	250.03	E10.29				
	250.1	E10.311				
	250.11	E10.319				
	250.12	E10.36				
	250.13	E10.37X1				
	250.2	E10.37X2				
	250.21	E10.37X3				
	250.22	E10.37X9				
	250.23	E10.39	-			
	250.3	E10.40				
	250.31	E10.51				
	250.32	E10.618				
	250.33	E10.620				
	250.4	E10.621				
	250.41	E10.622				
	250.42	E10.628				
	250.43	E10.630				
	250.5	E10.638				
	250.51	E10.641				
	250.52	E10.649				

Boehringer Ingelheim		
Protocol for non-interventional	studies based o	n existing data
BI Study Number 1237-0094		

Condition	ICD9	ICD10	ICD9 proc	ICD10 proc	HCPC S	CPT
	250.53	E10.65				
	250.6	E10.69				
	250.61	E10.10				
	250.62	E10.11				
	250.63	E10.21				
	250.7	E10.29				
	250.71	E10.311				
	250.72	E10.319				
	250.73	E10.36				
	250.8	E10.37X1				
	250.81	E10.37X2				
	250.82	E10.37X3				
	250.83	E10.37X9				
	250.9	E10.39				
	250.91	E10.40				
	250.92	E10.51				
	250.93	E10.618				
		E10.620				
		E10.621				
		E10.622				
		E10.628				
		E10.630				
		E10.638				
		E10.641				
		E10.649				
		E10.65				
		E10.69				
		E10.10				
		E10.11				
		E10.21				
Thyroid	226, 240.0,	D09.3, D34,				

Boehringer Ingelheim				
Protocol for non-interventional	studies ba	ased on	existing da	ta
BI Study Number 1237-0094				

 Study Number 1237-0094
 c30699487-01

 Proprietary confidential information © 2019 Boehringer Ingelheim International GmbH or one or more of its affiliated companies

Condition	ICD9	ICD10	ICD9 proc	ICD10 proc	HCPC S	CPT
disease	240.9, 241.0, 241.1, 241.9, 242*, 243, 244*, 245*, 246*, 790.94	D44.0, E01.1,E01.2, E01.8, E02, E03*, E04*, E05*, E06*, E07*, E01.0 E89.0				
Renal failure	403	I12.0				
	403.01	I12.9				
	403.1	N18.1				
	403.11	N18.2				
	403.9	N18.3				
	403.91	N18.4				
	585.1	N18.5				
	585.2	N18.6				
	585.3	N18.9				
	585.4	N17.0				
	585.5	N17.1				
	585.6	N17.2				
	585.9	N17.8				
	586	N17.9				
Autoimmune	135	D86.9				
disease	274.9	M10.9				
	275.49	E83.59				
	279.49	D89.89				
	283	D59.0				
	443	D59.1				
	448.9	I73.00				
	530.5	I73.01				
	555.9	I78.9				
	571.42	K22.4				

Boehringer Ingelheim		
Protocol for non-interventional	studies based	on existing data
BI Study Number 1237-0094		

Condition	ICD9	ICD10	ICD9 proc	ICD10 proc	HCPC S	CPT
	571.6	K50.90				
	576.1	K75.4				
	579	K74.3				
	696	K74.4				
	696.1	K74.5				
	710	K83.0				
	710.1	K90.0				
	710.2	L40.50				
	710.3	L40.54				
	710.9	L40.59				
	711.9	L40.0				
	712.19	L40.1				
	714	L40.2				
	714.3	L40.8				
	715.09	M32.10				
	715.11	M34.0				
	715.12	M34.1				
	715.13	M34.2				
	715.14	M34.81				
	715.15	M34.82				
	715.17	M34.83				
	715.18	M34.89				
	715.96	M34.9				
	719.42	M35.00				
	719.44	M35.01				
	719.45	M35.02				
	719.47	M35.03				
	719.49	M35.04				
	720	M35.09				
	721.9	M33.90				

Boehringer Ingelheim		
Protocol for non-interventional	studies based	on existing data
BI Study Number 1237-0094		

Condition	ICD9	ICD10	ICD9 proc	ICD10 proc	HCPC S	CPT
	725	M35.9				
	729.1	M00.9				
	729.5	M11.9				
	795.79	M06.9				
		M08.00				
		M15.0				
		M19.019				
		M19.029				
		M19.039				
		M19.049				
		M16.0				
		M16.10				
		M16.11				
		M16.12				
		M19.079				
		M19.91				
		M17.9				
		M25.529				
		M79.643				
		M79.646				
		M25.559				
		M25.579				
		M25.50				
		M45.9				
		M47.819				
		M35.3				
		M60.9				
		M79.1				
		M79.609				
		R76.0				

Boehringer Ingelheim		
Protocol for non-interventional	studies based	on existing data
BI Study Number 1237-0094		

 Study Number 1237-0094
 c30699487-01

 Proprietary confidential information © 2019 Boehringer Ingelheim International GmbH or one or more of its affiliated companies

Condition	ICD9	ICD10	ICD9 proc	ICD10 proc	HCPC S	CPT
		R76.11				
		R76.12				
		R76.8				
		R76.9				
Obesity	278	E65				
	278.01	E66.01				
	278.02	E66.2				
	278.03	E66.3				
	278.1	E66.9				
	278.2	E67.0				
	278.3	E67.1				
	278.4	E67.3				
	278.8	E67.8				
	V85.30	Z68.30				
	V85.31	Z68.31				
	V85.32	Z68.32				
	V85.33	Z68.33				
	V85.34	Z68.34				
	V85.35	Z68.35				
	V85.36	Z68.36				
	V85.37	Z68.37				
	V85.38	Z68.38				
	V85.39	Z68.39				
Alcohol use disorder	303	F10.159	94.46	HZ2ZZZ Z		
	303.01	F10.180	94.53	HZ30ZZ Z		
	303.02	F10.181	94.61	HZ31ZZ Z		
	303.03	F10.188	94.62	HZ32ZZ Z		
	303.9	F10.20	94.63	HZ33ZZ]	

Boehringer Ingelheim		
Protocol for non-interventional	studies based	on existing data
BI Study Number 1237-0094		

Condition	ICD9	ICD10	ICD9 proc	ICD10 proc	HCPC S	CPT
				Z		
	303.91	F10.21	94.67	HZ34ZZ Z		
	303.92	F10.229	94.68	HZ35ZZ Z		
	303.93	F10.259	94.69	HZ36ZZ Z		
		F10.27		HZ37ZZ Z		
		F10.280		HZ38ZZ Z		
		F10.281		HZ39ZZ Z		
		F10.288		HZ3BZZ Z		
		F10.959		HZ40ZZ Z		
		F10.980		HZ41ZZ Z		
		F10.99		HZ42ZZ Z		
		Z65.8		HZ43ZZ Z		
				HZ44ZZ Z		
				HZ45ZZ Z		
				HZ46ZZ Z		
				HZ47ZZ Z		
				HZ48ZZ Z		
				HZ49ZZ Z		
				HZ4BZZ Z		

Boehringer Ingelheim		
Protocol for non-interventional	studies based	on existing data
BI Study Number 1237-0094		

Condition	ICD9	ICD10	ICD9 proc	ICD10 proc	HCPC S	CPT
				HZ93ZZ Z		
				HZ96ZZ Z		
Tobacco use or cessation counselling	305.1* 649.0* 989.84 V15.82	Z72.0 F17.21 F17.210 F17.211 F17.218 F17.219 Z71.6			C9801 C9802 G0375 G0376 G0436 G0437 G8453 G8455 G8455 G8456 G8692 G9276 G9458 G9497 G9642 G9792 G9906 G9908 S9075 S9453 G9902 G9907	99406 99407
Cancer (excluding	140.xx – 195.xx	C00%-C76%,			09909	
basal cell carcinoma)	200.xx - 208.xx	C81%-C96%				
	196.xx - 199.xx	C77%-C80%				
	EXCLUDIN G:	EXCLUDIN G:				
	173.01	C44.01	1			
	173.11	C44.111	1			

Boehringer Ingelheim			
Protocol for non-interventional	studies based	on existing da	ata
BI Study Number 1237-0094			

Proprietary confidential information © 2019 Boehringer Ingelheim International GmbH or one or more of its affiliated companies

Condition	ICD9	ICD10	ICD9 proc	ICD10 proc	HCPC S	CPT
	173.21	C44.1121				
	173.31	C44.119				
	173.41	C44.91				
	173.51	C44.311				
	173.61	C44.319				
	173.71	C44.310				
	173.81	C44.510				
	173.91	C44.511				
		C44.519				
		C44.41				
		C44.81				
		C44.211				
		C44.212				
		C44.219				
		C44.611				
		C44.612				
		C44.619				
		C44.711				
		C44.712				
		C44.719				

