7.3 SUBJECTS

The study cohort will be formed based on the following entry criteria.

Inclusion Criteria:

- 1. At least one prescription for Tio+Olo or a LABA/LAMA/ICS combination between 1 January 2013 and 31 March 2019.
 - a. For Tio+Olo users, the first dispensing of Tio+Olo will be defined as the index date.
 - b. LABA/LAMA/ICS use can occur either in free or fixed combinations. The first date when all three medications are used based on either concurrent or overlapping dispensings in the pharmacy claims data will be defined as the index date.
- 2. At least one diagnosis of COPD at any time prior to the index date.
- 3. At least one year of continuous medical and pharmacy health plan eligibility prior to the index date will be required to allow a baseline period for the covariates and identification of new use of the study drugs.

Exclusion Criteria:

- 1. To increase the likelihood of a true diagnosis of COPD, we will exclude:
 - a. All patients less than 40 years of age on the index date, and
 - b. All patients with a diagnosis of asthma in the year prior to the index date
- 2. To limit the population to those without severe lung compromise outside of COPD, we will exclude individuals with lung cancer, interstitial lung disease, or lung transplant identified at any time prior to the index date
- 3. To restrict the cohort to new users of Tio+Olo or LABA/ICS, we will exclude any individual with use of either Tio+Olo, LABA/ICS, or LABA/LAMA/ICS combination therapy in free or fixed form for at least one year prior to the index date.

Outpatient laboratory data is available for a subset of patients. Some analyses will be further restricted to the subset of the population with at least one laboratory result showing circulating eosinophil levels within six months before the index date.

Individuals in the study cohort will be followed from the index date until the earliest of the date of a switch in treatment, addition of ICS for the Tio+Olo group, discontinuation of

COPD treatment, the end of the study period, or the end of continuous health plan eligibility. Main analyses will be further limited to the first year after cohort entry, with sensitivity analyses considering all available data.

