7.4.3 Covariates

Patient characteristics at baseline will be assessed for Tio+Olo and LABA/LAMA/ICS user overall and stratified by history of exacerbation, circulating eosinophils, subgroups defined by both exacerbation and eosinophil levels.

We will identify and describe the following demographic characteristics as of the index date:

- Sex
- Age (years, as both a categorical and a continuous variable)
- Calendar year of cohort entry

Proprietary confidential information © 2019 Boehringer Ingelheim International GmbH or one or more of its affiliated companies

- Season of index date (winter, spring, summer, fall)
- US census region of residence
- Insurance type (e.g., Commercial, Medicare)

Additional characteristics will be defined during the 12-month pre-index baseline period:

- Number of previous COPD treatments
- Specific previous COPD treatments
 - LAMA monotherapy
 - LABA monotherapy
 - ICS monotherapy
 - LAMA/ICS combination therapy
 - LABA/ICS combination therapy
- Previous acute COPD exacerbation (measured both overall and in the 30 days prior to cohort entry), categorized as 0, 1, or 2+.
 - All exacerbations (Moderate+Severe)
 - ED visits or dispensings of inhaled corticosteroids/antibiotics (Moderate)
 - Hospitalizations (Severe)
- Use of other respiratory drugs in the 12-month pre-index period:
 - Short-acting beta-agonists
 - Anticholinergics
 - Methylxanthines
 - Muscarinic antagonists
 - Short-acting muscarinic antagonists
- Use of antibiotics for a respiratory condition (e.g., azithromycin)

Chronic comorbidities will be defined using diagnoses identified during all available data prior to the index date, and will include:

- Cardiovascular disease
- Charlson comorbidity index
- Diabetes
- Thyroid disease
- Renal failure
- Autoimmune disease
- Pneumonia
- Obesity*
- Alcohol use disorder*
- Tobacco use or cessation counselling*
- Cancer (excluding basal cell carcinoma)
- * We anticipate limited capture of lifestyle variables known to be risk factors and potential confounders, including obesity, smoking status and excessive alcohol consumption. Although we will describe them as identified in the HIRD, bias analyses to examine the extent to which residual confounding may impact results are also planned.

Additionally to the covariates defined above, we will use the high-dimensional approach to identify variables entering a time-conditional propensity score.

Boehringer Ingelheim	

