7.5 DATA SOURCES

This study will be conducted using the HIRD, a large administrative healthcare database maintained by HealthCore for use in health outcomes and pharmacoepidemiologic research. The HIRD includes longitudinal medical and pharmacy claims data from health plan members across the United States (US). Member enrolment, medical care (professional and facility claims), outpatient prescription drug use, outpatient laboratory test result data, and health care utilization may be tracked for health plan members in the database dating back to January 2006, and with diagnoses recorded in International Classification of Disease, Version 10 (ICD-10) since October, 2015. Laboratory result data are additionally available for those tests that have been performed using two large, national reference laboratories (Quest and LabCorp) [R14-4278]. The database has been used for the study of numerous diseases, including studies of COPD [R19-2324; R19-2321; R19-2323; R19-2322; P15-11025; P14-12233]

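### Three covariate code lists in Annex 3.3 (diabetes, the hypertension part of cardiovascular disease, tobacco) do not carry over from ICD-9 to ICD-10, and the planned balance check cannot show it

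*Combined protocol and SAP*

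**What the plan says.** Annex 3.3 presents itself as the full set of covariate codes, and Annex 1 lists no stand-alone document that could hold another version.

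- **Diabetes.** The ICD-9 column runs through the whole 250 category. Every entry in the ICD-10 column begins with E10.
- **Cardiovascular disease.** The ICD-9 column contains "426.xx 428.xx 401.xx- 405.xx", so all of 401-405 counts. The ICD-10 column has "I50.%% I11.%; I13.%; O10.1%; O10.3" at the corresponding place.
- **Tobacco.** ICD-9 is "305.1* 649.0* 989.84 V15.82". ICD-10 is "Z72.0 F17.21 F17.210 F17.211 F17.218 F17.219 Z71.6". HCPCS codes and CPT 99406 and 99407 are listed beside them.

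On timing, Section 7.3 admits patients with "At least one prescription for Tio+Olo or a LABA/LAMA/ICS combination between 1 January 2013 and 31 March 2019". Section 7.5 describes a database "with diagnoses recorded in International Classification of Disease, Version 10 (ICD-10) since October, 2015" and reaching back to January 2006. Section 7.4.3 sets the look-back: "Chronic comorbidities will be defined using diagnoses identified during all available data prior to the index date".

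Section 7.9.1 puts the pre-specified covariates into a high-dimensional propensity score with data-derived variables, and treats a standardized difference above 0.10 as imbalance.

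**The concern.** A covariate flag should mean the same thing whichever coding system was in force. Here a patient with type 2 diabetes counts as diabetic if the diagnosis was ever billed under ICD-9, but not if all of that patient's claims are in ICD-10. A former smoker known only through a history code is treated the same way. The flag becomes partly a marker of entry date and length of enrolment.

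Two things are at stake. First, the baseline table will be wrong for later entrants. Second, the plan judges confounding control by comparing these same flags between arms. If the flag is faulty, the weighted arms can agree on it and still differ on the underlying condition, and the 0.10 threshold would not reveal that.

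**Working it through.** The plan states no figure on this point, so there is none to reproduce. The meanings of individual codes are general classification knowledge; the protocol does not give them.

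**1. The lists side by side**

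| Row | ICD-9 | ICD-10 | Missing from ICD-10 |
|---|---|---|---|
| Diabetes | 250.00-250.93, all 40 codes | 53 entries, 25 distinct, all E10 | E11, E13 |
| Hypertension within cardiovascular disease | 401-405 | I11, I13, O10.1, O10.3 | I10, I12, I15 |
| Tobacco | 305.1, 649.0, 989.84, V15.82 | Z72.0, F17.21x, Z71.6 | history code; other F17.2x |

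The diabetes run from E10.10 to E10.69 is printed twice and then restarts with three codes: 22 codes appear twice and 3 appear three times (22 × 2 + 3 × 3 = 53). Complete runs repeated in order indicate a copying error rather than a damaged table. I12.0 and I12.9 appear only under renal failure.

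**2. Timing**

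- Entry runs from January 2013 to March 2019: 33 months before October 2015 and 42 from then on, 75 in all.
- Only one year of prior eligibility is required. From October 2016 (30 of the 75 months) a patient with that minimum has no ICD-9 history at all.
- Patients enrolled for longer keep any flag earned under ICD-9. The change is therefore gradual, not a clean break in October 2015.

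**3. Effect on the diabetes flag in later entrants (assumed inputs)**

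Let P be true prevalence (20-30%), s the share of diabetic patients who ever receive an E10 code (5-20%), and h the share of diabetic later entrants who already have a 250.xx record. Flag prevalence = P × (h + (1 − h) × s).

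- h = 0: from 0.20 × 0.05 = 1% to 0.30 × 0.20 = 6%. Among the unflagged, 17-29% truly have diabetes.
- h = 0.5: from 0.20 × 0.525 = 10.5% to 0.30 × 0.60 = 18%.

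**4. Hidden imbalance if the flag's sensitivity differs by arm (assumed inputs)**

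Take true prevalence 28% in both arms, sensitivity 0.30 for Tio+Olo and 0.60 for triple therapy, no false positives, and the triple arm weighted to the Tio+Olo arm on this flag alone.

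- Flag prevalence: 0.28 × 0.30 = 0.084 and 0.28 × 0.60 = 0.168.
- True diabetes among unflagged triple users: (0.28 − 0.168)/(1 − 0.168) = 0.135.
- True diabetes in the weighted triple arm: 0.084 + 0.916 × 0.135 = 0.207.
- Standardized difference: (0.28 − 0.207)/√[(0.28 × 0.72 + 0.207 × 0.793)/2] = 0.17, while the flag itself shows 0.

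With prevalence 20-35% and sensitivities 0.2-0.4 against 0.5-0.6, the result runs from 0.045 (20%, 0.4 vs 0.5) to 0.255 (35%, 0.2 vs 0.6). None of this allows for adjustment for calendar time. If that adjustment brings the sensitivities closer, to 0.30 against 0.35 or 0.40 at 28% prevalence, the result is 0.03 or 0.05.

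**5. Effect on the hazard ratio**

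Use the single-confounder factor [p1(RR − 1) + 1]/[p0(RR − 1) + 1], with p1 = 0.207 (triple), p0 = 0.28 (Tio+Olo) and an assumed diabetes-outcome RR of 1.2-1.5.

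- RR 1.2: 1.041/1.056 = 0.99.
- RR 1.5: 1.104/1.140 = 0.97.

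Even the unadjusted case in step 4 moves the hazard ratio by only about 1-3% through diabetes.

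**The case against.** The strongest defence is that the same lists apply to both arms, so the hazard ratio is biased only if the arms differ in entry date or enrolment history. The documents give no such distribution. The plan also has several layers of protection: calendar year of entry is a covariate, the score is described as time-conditional, and data-derived variables may pick up the missing codes. The Charlson index is a separate covariate that normally counts diabetes, and Annex 3.3 does not show it using the E10 block. All of this stands, and it limits the likely bias. It does not repair the named flags or the table built on them.

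Other points also narrow the concern:

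- The cardiovascular flag keeps ischaemic disease, arrhythmia, conduction disorders, heart failure, vascular disease and lipid disorders in both systems, so the hypertension gap is diluted.
- Tobacco is not reduced to cigarette dependence: Z72.0, Z71.6 and the procedure codes remain. Section 7.4.3 already expects poor capture of smoking, obesity and alcohol, and plans bias analyses. That caveat does not cover diabetes or hypertension, and it does not mention the mismatch.

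A reader might infer that the primary hazard ratio is materially biased, or take 0.17 as an estimate of imbalance. The documents support neither: the sensitivities behind 0.17 are assumed, and that calculation ignores the planned adjustment. A reader might also want to add the autoimmune row (joint and limb pain codes) and the obesity row (vitamin-excess codes). Those codes stand in both columns, so they create no break in October 2015.

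**Conclusion.** The three ICD-10 lists are wrong as written and should be corrected. The omissions can be verified from Annex 3.3; only the meanings of the codes come from outside the documents.

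The firm consequence is that the diabetes flag, and in part the tobacco flag, depends on having claims from before October 2015. Diabetes and past smoking will be understated in later entrants, and the 0.10 criterion applied to those flags cannot detect it.

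The effect on the hazard ratio is not established. It requires a difference between arms in entry date or enrolment history, and the planned adjustments probably keep it small. For diabetes alone the illustration gives a factor of 0.97-0.99 without those adjustments. The effect of the tobacco gap was not quantified. This should be fixed before the score is fitted, but it does not by itself undermine the primary analysis.

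**What to change.** - Diabetes: replace the repeated E10 block with E10, E11 and E13.
- Cardiovascular disease: add I10, I12 and I15 to the ICD-10 list. Deleting ICD-9 401 and 403-405 instead would not harmonise the row, because I13 would then lose its counterpart, 404.
- Tobacco: add the ICD-10 code for history of nicotine dependence and the remaining F17.2x codes.
- Before fitting the propensity score, tabulate the prevalence of each flag by month and arm across October 2015, and investigate any step.

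The cost is a code-list edit, a rerun of the covariate extraction and one descriptive table. No new data are needed.

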7.9 DATA ANALYSIS

7.9.1 Main analysis

All analyses will be presented for each group (Tio+Olo vs LABA/LAMA/ICS) overall and stratified as follows:

- History of exacerbation: 0 inpatient and 0-1 outpatient events
- History of exacerbation: 1 + inpatient or 2 + outpatient events
- Circulating eosinophils: B-Eos < 300 ug/mL
- Circulating eosinophils: B-Eos 300 ug/mL+
- History of exacerbation: 0 inpatient and 0-1 outpatient events & circulating eosinophils: B-Eos < 300 ug/mL
- History of exacerbation: 0 inpatient and 0-1 outpatient events & circulating eosinophils: B-Eos 300 ug/mL +

We will first describe formation of the study cohort. Patient characteristics at baseline in patients treated with Tio+Olo and patients treated with LABA/LAMA/ICS will be described using standard descriptive statistics. Because eosinophil levels may vary based on exacerbation, we will also provide a count and percentage of the number of individuals whose eosinophil results were recorded within 30 days of an exacerbation event.

High-dimensional propensity scores including both pre-specified and data-derived variables will then be calculated. We will use fine stratification and reweighting of the exposure propensity score to control for measured covariates [R19-3030]. Balance of patient characteristics between the cohorts will be described before and after propensity score application and compared using standardized differences (in the crude population and the reweighted pseudo-population). Standardized differences greater than 0.10 (10%) will be taken to indicate imbalance and further refinement approaches will be applied.

For the analysis of the primary objective, a Cox proportional hazard regression model will be used to perform an as-treated analysis that assesses the effect of current use of LABA-LAMA-ICS combination versus the Tio+Olo combination on the risk of a first COPD exacerbation. It will provide an estimate of the hazard ratio (HR) of a COPD exacerbation associated with LABA-LAMA-ICS use relative to Tio+Olo use, along with 95% confidence intervals (CI).Current use will be defined based on the days supply during the period of overlap, allowing a grace period of 15 days following the end of days supply to account for intermittent use. This approach allows consideration of exposure as time-dependent, accounting for the changes in exposure during the follow-up. In particular, this analysis excludes patients stopping one or more of the drugs prior to the index date.

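### The single cardiovascular covariate pools heart failure with lipid disorders and other unlike conditions, so its balance check cannot show imbalance in heart failure, and its hypertension codes differ between ICD-9 and ICD-10

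*Combined protocol and SAP*

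**What the plan says.** Section 7.4.3 names a single item, "Cardiovascular disease", in its comorbidity list. The look-back is the full record: "Chronic comorbidities will be defined using diagnoses identified during all available data prior to the index date, and will include". Thyroid disease and renal failure each have their own entry in that list; heart failure does not.

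The only definition is one row of Annex 3.3. Its ICD-9 cells read "410.xx- 414.xx 427.xx; 785.0; 785.1 426.xx 428.xx 401.xx- 405.xx 440.xx; 441.xx; 442.xx" and continue on the next page with "443.xx 272.x 393-398; 421.x; 422.xx; 746.0x-746.7". Its ICD-10 cells include "I50.%% I11.%; I13.%; O10.1%; O10.3" and "E78.%% I05.%- I09.%%; I33.%-I39; Q22.%, Q23". The row also carries ICD-9 procedure codes 37.7x-37.8x and 37.94-37.99. No sub-indicators are named.

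Section 7.9.1 gives the diagnostic, with refinement to follow if it is failed: "Standardized differences greater than 0.10 (10%) will be taken to indicate imbalance". Sections 7.4.3 and 7.9.1 also plan a Charlson index and a high-dimensional propensity score that adds data-derived variables to the pre-specified ones.

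On coding, Section 7.5 describes a database "with diagnoses recorded in International Classification of Disease, Version 10 (ICD-10) since October, 2015". Section 7.3 sets cohort entry from January 2013 to March 2019, so the change falls inside the entry window.

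**The concern.** In standard ICD nomenclature (the annex does not label its groups) the row covers ischaemic disease (410-414), arrhythmia and conduction disorders (426, 427, 785.0, 785.1), heart failure (428/I50), hypertension (401-405), arterial disease (440-443), lipid disorders (272/E78), and valvular, inflammatory or congenital heart disease. A patient with one lipid claim falls in the same category as a patient with heart failure. A standardized difference for the pooled item therefore says little about any one component.

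Heart failure is the component of most interest, because it plausibly raises pneumonia admissions (the secondary outcome) and perhaps COPD-coded ED visits and admissions (part of the primary outcome). If it also differed between the arms, the hazard ratio could be biased without the 0.10 rule triggering refinement. The planned bias analyses in Section 7.4.3 are described for lifestyle factors and would not obviously cover this.

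Separately, the ICD-9 and ICD-10 columns do not match on hypertension, so the covariate does not measure the same thing throughout the study.

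**Working it through.** The documents state no figure on this point, so there is nothing to reproduce. The calculation shows the mechanism and its possible size.

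**Inputs.** From the documents: the code row, the 0.10 limit, and the orientation of the hazard ratio in Section 7.9.1 (triple therapy relative to Tio+Olo). Assumed: heart-failure prevalence by arm, prevalence of the other pooled conditions (equal in both arms and independent of heart failure), an outcome hazard ratio for heart failure of 1.5 or 2, and no other variable in the score capturing heart failure.

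**Formulas.**
- Standardized difference (SMD) = (p1 − p0) / √{[p0(1 − p0) + p1(1 − p1)] / 2}
- Bias factor on the hazard ratio = [1 + p1(HR − 1)] / [1 + p0(HR − 1)]

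**Base illustration: heart failure 24% vs 18%, pooled item equal in both arms.**
- SMD = 0.06 / √[(0.1824 + 0.1476)/2] = 0.06 / 0.406 = 0.148, above 0.10, while the pooled item shows 0.
- Factor at outcome HR 1.5 = 1.12 / 1.09 = 1.028.
- Factor at outcome HR 2 = 1.24 / 1.18 = 1.051.
- If heart failure is commoner in the Tio+Olo arm, the factors invert: 1.09 / 1.12 = 0.973 and 1.18 / 1.24 = 0.952.
- For scale, Section 7.7 refers to a hazard ratio of 0.85. On the log scale the two factors are about 17% and 31% of that effect.

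**Does it depend on the pooled item being very common?** Take heart failure at 15% vs 20% (SMD 0.132). Pooled prevalence = 1 − (1 − heart failure)(1 − other). One arm is then weighted so that the pooled item balances exactly. For other = 50%, the 15% becomes 0.15 × 0.60 / 0.575 = 15.7%.

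| Other conditions | Pooled item | SMD of pooled item, unweighted | Heart-failure SMD after exact balance | Factor at HR 1.5 / 2 |
|---|---|---|---|---|
| 30% | 40.5% vs 44.0% | 0.071 | 0.096 | 1.017 / 1.032 |
| 50% | 57.5% vs 60.0% | 0.051 | 0.114 | 1.020 / 1.038 |
| 80% | 83.0% vs 84.0% | 0.027 | 0.127 | 1.022 / 1.042 |
| 95% | 95.8% vs 96.0% | 0.013 | 0.131 | 1.023 / 1.043 |

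The pooled item never reaches 0.10, and most of the heart-failure difference survives in every row.

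**Range.** With 10% vs 13% the factors are 1.012-1.014 (HR 1.5) and 1.022-1.027 (HR 2), and the heart-failure SMD is below 0.10 anyway. With 15% vs 25% they are 1.034-1.046 and 1.063-1.086. In that case the pooled item itself exceeds 0.10 when other conditions are 50% or less.

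**Coding eras, side by side.** ICD-9 hypertension is 401-405. The ICD-10 cells give only I11, I13, O10.1 and O10.3; I10, the counterpart of 401, is absent. A patient who enters before October 2015 is classified on ICD-9 alone. A patient who enters in March 2019 with one year of history is classified on ICD-10 alone, where ordinary hypertension does not count. Patients in between depend on how far back their record goes. Lipid codes are pooled in both eras.

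**The case against.** The strongest reply is that the pooled item is not the only control. A diagnosis held by about a fifth of patients and imbalanced between arms is a likely candidate for data-derived selection, and the Charlson index may carry it too. This stands, and it is why the figures above are upper-end for the gap assumed. It does not remove the point, because neither route guarantees a heart-failure term or balance row. The contents page lists an Annex 3.4 on statistical considerations that is not in the text available, so I count no absent score setting against the plan.

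It is also fair to say that both arms receive a LABA and a LAMA. The contrast is the inhaled corticosteroid, and nothing in the documents shows that heart failure drives that choice. The size and direction of any imbalance are unknown.

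A reader might infer more than the documents support:
- *That nearly every patient is positive.* No prevalence is given, and the table shows the point does not need it.
- *That any blood-pressure claim sets the indicator.* In ICD-10 an ordinary hypertension claim does not, since I10 is not listed.
- *That breathlessness visits caused by heart failure count as outcomes.* Section 7.4.2.1 requires a COPD diagnosis, or an antibiotic and an oral corticosteroid dispensed on the same day.
- *That data-derived selection breaks down among the 868 Tio+Olo users (226 + 105 + 537) with a high exacerbation history.* Section 7.9.1 specifies a repeated score only for the laboratory subset, so re-selection in that stratum is not stated.
- *That a heart-failure imbalance would certainly go unseen.* Section 7.9.1 checks patient characteristics without restricting them to the pre-specified list; a heart-failure row is neither promised nor excluded.

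**Conclusion.** The point holds as a minor one. Annex 3.3 pools unlike conditions under one label, and on the natural reading (one bullet, one row, coding not spelled out) it is a single indicator. Balance on it is not evidence of balance on heart failure or any other component. The hypertension codes are inconsistent between coding systems, and the switch falls inside the entry window.

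The size rests entirely on assumed prevalences and outcome effects, and on nothing else in the score capturing heart failure. At 24% vs 18% the factor is about 1.03 to 1.05; over the wider grid it is 1.01-1.05 at an outcome hazard ratio of 1.5 and 1.02-1.09 at 2. The documents do not support a claim that the planned hazard ratio will be biased by these amounts. The actual residual bias is likely smaller.

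**What to change.** In Section 7.4.3 and Annex 3.3, replace the single item with seven pre-specified indicators:
- heart failure (428/I50);
- ischaemic heart disease (410-414/I20-I25);
- arrhythmia and conduction disorders (426-427/I44, I45, I47-I49, with 785.0, 785.1 and procedure codes 37.7x-37.8x and 37.94-37.99);
- hypertension;
- arterial disease (440-443/I70-I73);
- lipid disorder (272/E78);
- valvular and other heart disease (the remaining codes).

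Align the hypertension lists by adding I10 as the counterpart of 401, and check the counterparts of 402-405 at the same time. Without this, a separate hypertension indicator would still change meaning in October 2015. Enter all seven in the propensity score, and apply the 0.10 rule to each, including in the laboratory subset where the score is repeated.

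The cost is a wording change and six more binary terms, negligible against the 5,458 Tio+Olo users expected in the abstract (5,469 in the Section 7.7 table). Apart from the added hypertension codes, the codes are already in the row, and no new data source is needed.
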